6. ANALYTIC DEFINITIONS

Baseline Measurements will be the last measurement for the corresponding endpoint prior to the first dose of study drug.

Age at Baseline is the last non-missing age collected before the first dose of study drug.

Body Mass Index is calculated as (Weight in kg / (Height in meter)²). The last non-missing weight and height collected before the first dose of study treatment will be used to calculate the baseline body mass index.

Study Drug Exposure is calculated as number of days from first dose day to last. That is:

Study Drug Exposure = Last Study Drug Date – First Study Drug Date + 1.

Study Drug Compliance (%) for a participant is calculated as: 100*total number of doses taken/total number of doses the participant was supposed to have taken during the treatment period. That is, 100*total number of doses taken ÷ (8* Study Drug Exposure [in Days]).

A Treatment-Emergent Adverse Event (TEAE) is any adverse event that occurs on or after first dosing and up through Day 28.

COVID-19 Rescue Treatments that are defined as any treatment approved under NDA or Emergency Use Authorization (EUA) for COVID-19 or off label medications given as direct treatment of COVID-19.

Concomitant Medication will be defined as the medications used on/after the first dose of study drug or started before first dose of study drug and continued during the study.

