# 6.3 Dosing Period (Day 1 through Day 8)

After provision of informed consent, participants who satisfy all necessary eligibility criteria will receive doses of ANA001 or matching placebo to begin within approximately 36 hours of site screening and as soon as possible following hospital presentation.

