- Daily administration of study drug (ANA001 or matching placebo). Study drug should be taken with a meal (or NG/OG/PEG tube feeding if applicable). Total duration of study drug administration is a 7-day course of treatment (i.e., 14 scheduled doses comprised of 56 capsules in total). Participants may be discharged before completing 14 doses and are to be given dosing instructions, the remainder of their therapy, and a diary to record all study drug doses taken.
- Daily serum chemistry (pre-dose), including blood urea nitrogen (BUN), creatinine, sodium, potassium, chloride, carbon dioxide, glucose, direct bilirubin, total bilirubin, alkaline phosphatase (ALP), aspartate aminotransferase (AST), alanine aminotransferase (ALT).

- Daily hematology and coagulation tests (pre-dose) including a complete blood count (CBC), which consists of hematocrit, hemoglobin, total WBC count with a 5-part differential, platelet count, plus a partial thromboplastin time (aPTT), prothrombin time (PT), and an international normalized ratio (INR).
- D-dimer, CRP, and ferritin (to be collected pre-dose on Day 4 and Day 8 only) for central laboratory testing. Cardiac troponin and LDH (to be collected Day 8 or EOT) for central laboratory testing.
- NP swab for confirmation of SARS-CoV-2 with RT-PCR (local site laboratory) per site SOC if part of standard-of-care.
- NP swab for SARS-CoV-2 testing with RT-PCR (to be collected on Day 4 and 8) for central laboratory testing.
- PK sample collection: Study Part 1 Only: See Appendix 6 for PK sample collection schedule. Refer to the Central Laboratory Manual for additional sample collection and processing instructions (Day 1, 2, 3 or Day 4). PK samples should be collected in relation to the morning dose of study drug.
- Daily WHO Ordinal Scale for Clinical Improvement score (Appendix 1) assessment should be collected/recorded daily and any time the WHO Ordinal Scale for Clinical Improvement score changes. The WHO Ordinal Scale for Clinical Improvement should be recorded with the corresponding date and time of assessment (if unchanged) or with the date and time reflecting the numerical change in the score (if changed).
- Chest X-ray per local standard-of-care.
- Daily AE assessment.
- All systemic concomitant medications (Section 7.4).
- SOFA score (to be performed daily only for participants who are admitted in the ICU; Appendix 3).
- Blood for exploratory tests (e.g., IL-6, tissue factor, MCP-1 and IP-10) on Day 8.

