#### 7.1.1.2 Dosing and Administration

ANA001 will be administered as 1,000 mg (4 capsules; 250 mg each) PO BID for 7 consecutive days and should be given with a meal. If the participant requires mechanical ventilation over the course of the study, niclosamide may be administered via NG, OG, or PEG tube and, if possible, should be administered with a scheduled NG, OG, or PEG feeding. Please refer to the study Pharmacy Manual for additional dosing and study drug administration information.

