7.3 Treatment Exposure and Compliance

Number of doses received, treatment duration (in days) and percent of treatment compliance and compliance category (<80%, 80%-120%, >120%) will be summarized by treatment group for all participants in the Full Analysis Set.

COVID-19 rescue medications will be classified according to the anatomical therapeutic chemical (ATC) codes in the World Health Organization Drug (WHODRUG) dictionary; version B3 WHO Drug DDE – March 2020. The incidence rate of each classified medication will be tabulated by treatment group for all participants in the intent-to-treat population.

Concomitant medications will be classified and tabulated in a manner similar to rescue medications.

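### SAP section 6 computes the compliance denominator from calendar dates between first and last dose taken, so an early stopper can score 100% and a perfect evening-start course scores 87.5%

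*SAP*

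**What the plan says.** SAP section 6 gives compliance twice. In words it is "100*total number of doses taken/total number of doses the participant was supposed to have taken during the treatment period". The next sentence turns this into "100*total number of doses taken ÷ (8* Study Drug Exposure [in Days", where exposure is "Study Drug Exposure = Last Study Drug Date – First Study Drug Date + 1". SAP section 7.3 summarises the percentage and a "compliance category (<80%, 80%-120%, >120"%) by treatment group.

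The planned amount is fixed elsewhere. Protocol 7.1.1.2 states "ANA001 will be administered as 1,000 mg (4 capsules; 250 mg each) PO BID for 7 consecutive days", and Protocol 6.3.2 gives "14 scheduled doses comprised of 56 capsules in total". SAP section 3 also defines the course as 14 doses given twice daily. Protocol 6.3 is headed "Dosing Period (Day 1 through Day 8"), and the schedules in both documents mark drug administration on Days 1 to 8, with study days counted as calendar days. Protocol 6.6.1.2 foresees stopping study drug before the course is complete.

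**The concern.** The words and the formula agree only when first and last dose lie exactly 7 calendar dates apart, counted inclusively. They part in two ordinary situations.

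- **Early stopping.** The denominator ends at the last dose taken, so the rest of the planned course is never counted as missed.
- **Evening start.** A twice-daily course of 14 doses that begins in the evening covers 8 dates. The formula charges two doses to each date, including the half-used first and last.

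This is separate from the question whether 8 per day means doses or capsules, and it survives whichever way that is resolved. At stake is whether the compliance percentage and its categories mean what SAP section 6 says they mean, in a part of the study whose primary objective is safety and tolerability.

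**Working it through.** **Inputs.** Exposure E = last date − first date + 1, and compliance = 100 × amount taken / (8 × E), both from SAP section 6. The planned course is 4 capsules twice daily for 7 days (Protocol 7.1.1.2), i.e. 14 doses or 56 capsules (Protocol 6.3.2). The categories are in SAP section 7.3.

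**Planned figure reproduced.** 4 × 2 × 7 = 56 = 8 × 7. The constant 8 therefore fits capsules. Taken literally with doses, a full course would score 14/(8 × 7) = 25.0% from a morning start or 14/(8 × 8) = 21.9% from an evening start, so the unit must be settled first. After that, n doses score 100 × 4n/(8E) = 100 × n/(2E), whether counted in capsules over 8 or doses over 2.

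**(a) Early stopping.** For n consecutive doses with none missed, E is n/2 rounded up for a morning start, and n/2 rounded down plus 1 for an evening start.

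| Doses taken | Start | E | SAP formula | Share of 14 |
|---|---|---|---|---|
| 2 | morning | 1 | 2/2 = 100% | 14.3% |
| 6 | morning | 3 | 6/6 = 100% | 42.9% |
| 10 | morning | 5 | 10/10 = 100% | 71.4% |
| 1 | either | 1 | 1/2 = 50.0% | 7.1% |
| 4 | evening | 3 | 4/6 = 66.7% | 28.6% |
| 8 | evening | 5 | 8/10 = 80.0% | 57.1% |
| 11 | either | 6 | 11/12 = 91.7% | 78.6% |

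Taking n = 1 to 13 with both start times gives 26 patterns.

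- Exactly 100%: 6 patterns (morning start, n = 2, 4, 6, 8, 10, 12). The other 20 score from 50% to 92.9%.
- Below 80% of the planned course (n up to 11, since 11/14 = 78.6%): 22 patterns.
- Of those 22, placed in 80%-120%: morning start n = 2 and 4 to 11 (9 patterns), evening start n = 5 and 7 to 11 (6 patterns), so 15. The other 7 fall below 80%.

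These are counts of patterns, not forecasts of participants.

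**(b) Evening start.**

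- Full course: 1 + 6 × 2 + 1 = 14 doses over 8 dates. Due by formula: 2 × 8 = 16. Score 14/16 = 87.5% (capsules 56/64). A morning start gives 14/14 = 100%.
- 12 of 14 doses, Day 8 dose taken and both missed doses earlier: 12/16 = 75.0%, against 12/14 = 85.7%. The category changes to below 80%.
- 12 of 14 doses with the Day 8 dose among those missed: 7 dates, 12/14 = 85.7%, so no distortion.

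**(c) On-treatment reading.** Suppose doses are due only until the participant stops, and stopping is recorded before the next dose falls due. All 26 patterns then have no missed dose and should score 100%. The formula gives 100% for 6 and less for 20. Four doses from an evening start, all taken, score 66.7%.

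**The case against.** The best defence is that the formula measures adherence while on treatment. SAP section 6 does not define the treatment period, and it presents the formula as a restatement of the words. Someone taken off drug for an adverse event was arguably not due any more doses, and dividing by 14 for everyone merges adherence with discontinuation. That is a defensible choice for early stoppers. It does not rescue the calendar-date count, which gives wrong values under that reading too, as (c) and the 87.5% show.

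The defence on consequences largely stands. A reader might infer that an excess of early stopping on ANA001 would vanish from the report. The documents do not support that. SAP 7.3 tabulates doses received and length of treatment by arm beside compliance, so someone who stops after two morning-start doses still appears as 2 doses and 1 day. SAP 7.1 reports early discontinuation with reasons by arm, and SAP 4.3 and 7.6.1 cover adverse events leading to discontinuation.

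Two other inferences also go too far. Early stoppers do not all score 100%: that needs a morning start, a complete last day and no missed dose. Nor are evening starters who take every dose classed as non-compliant, because 87.5% lies within 80%-120%.

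**Conclusion.** The point holds as a definitional error of limited reach. The formula does not compute the quantity SAP section 6 describes, and no other section corrects it. The early-stop effect can change the reported category. The evening-start effect lowers the continuous summary and changes the category only in cases such as 12 of 14 doses with the Day 8 dose taken and both misses earlier. With 30 participants planned per arm in Part 1, each misclassified participant moves a category by 1/30 = 3.3 percentage points.

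A reader might go further and doubt the Part 1 tolerability conclusions. The documents do not support this. The percentage is a descriptive exposure summary. The primary parameters are adverse events, deaths, discontinuations due to adverse events, vital signs and laboratory values. No test uses the percentage, and the Per Protocol Set in Protocol 9.2 carries no compliance threshold.

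The figures assume that the dose-or-capsule unit has been made consistent. The documents give no frequency of evening starts or early stops, so the number of participants affected is unknown.

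**What to change.** In SAP section 6, compute compliance as 100 × doses taken / 14 (equivalently capsules taken / 56) for every dosed participant, whatever the date of the last dose. Two of 14 doses then scores 14.3%, six of 14 scores 42.9%, and a full course scores 100% whatever the time of its first dose.

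If adherence while on treatment is also wanted, give it its own label, report it separately, and count scheduled dose occasions from first dose to recorded discontinuation instead of calendar dates. Correct the per-day unit in the same edit, since it sits in the same sentence.

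The planned-course measure needs one changed line and no new data, because the amount taken is already the numerator. The cost is that reported compliance becomes less favourable for participants who stop early.

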3. STUDY DESIGN

This is a 2-part, multicenter, randomized, placebo-controlled clinical study of ANA001 in patients with moderate and severe COVID-19. The study duration for each participant will be approximately 62 days, including a 36-hour screening window. Screening and Day 1 may occur on the same day if screening criteria are met to confirm participant eligibility. After provision of informed consent, participants who satisfy all inclusion and no exclusion criteria will be randomized in a 1:1 ratio to be treated with ANA001 1000 mg BID or matching placebo. Randomization of participants will be stratified by oxygenation (SpO2 > 93 and < 98% on room air versus \leq 93% on room air), diarrhea (presence versus absence), and age (< 65 and \geq 65). Participants will be dosed within 36 hours of screening and as soon as possible following hospital presentation.

* An independent DMC will review Part 1 and Part 2 data on an ongoing basis until the study is complete.

Participants will receive capsules of ANA001 or matching placebo for 7 consecutive days (defined as 14 doses administered BID) according to the assignment made by the randomization and trial supply management (RTSM) system. Additionally, participants will receive continued standard of care therapy (per study site policies or guidelines). Dosing will continue until the treatment course is completed. If the participant requires mechanical ventilation or for any other reason is unable to swallow oral medication over the course of the study, ANA001 will be administered via nasogastric (NG) or orogastric (OG) tube in accordance with the appropriate section in the study Pharmacy Manual. If the participant is discharged prior to completing the

treatment course, the remaining study drug will be dispensed for at-home administration. Every effort will be made to complete the remaining study assessments for participants who are not able to complete the 7-day consecutive course of study drug.

Upon successful completion of Part 1, the safety and efficacy of ANA001 1,000 mg PO BID for 7 consecutive days will be evaluated in a larger population of patients in Part 2.

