7.1 Participant Disposition and Protocol Deviations

Participants' disposition will be described by reporting the number of randomized participants, the number and percentage of participants randomized but not treated, number and percentage of participants in each of the stratification factors, the number and percentage of participants in each analysis set by treatment group. Additionally, the number and percentage of participants who completed treatment and those who discontinued treatment early along with the reason for early treatment discontinuation as well as the number and percentage of participants who completed the study or withdrew early from the study along with the reason for early withdrawal from the study will be presented by treatment group.

Number and percentage of participants randomized by site number and investigator name will also be reported by treatment group.

Incidence of major protocol deviation will be tabulated by protocol deviation category and deviation for all participants in the Full Analysis Set.

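### The SAP compliance formula divides doses by capsules per day, so no participant dosed at or below schedule can score above 25.0% in the Part 1 compliance table

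*SAP*

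**What the plan says.** SAP section 6 (Analytic Definitions) defines compliance twice in succession. In words it is "100*total number of doses taken/total number of doses the participant was supposed to have taken during the treatment period". The next sentence restates it: "That is, 100*total number of doses taken ÷ (8* Study Drug Exposure [in Days". The exposure term counts calendar dates: "Study Drug Exposure = Last Study Drug Date – First Study Drug Date + 1".

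SAP section 3 sets the schedule: capsules are given "for 7 consecutive days (defined as 14 doses administered BID) according to the assignment". Protocol 7.1.1.2 says what a dose consists of: "ANA001 will be administered as 1,000 mg (4 capsules; 250 mg each) PO BID for 7 consecutive days". Protocol 7.1.2.2 gives placebo in the same number of capsules. Protocol 6.3.2 states both totals side by side: "i.e., 14 scheduled doses comprised of 56 capsules in total". The study drug row is marked through Day 8 in Protocol Table 1 and in SAP Appendix A, and the heading of Protocol 6.3 runs the dosing period from Day 1 to Day 8.

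SAP 7.3 tabulates the result by treatment group for the Full Analysis Set: "Number of doses received, treatment duration (in days) and percent of treatment compliance and compliance category (<80%, 80%-120%, >120" percent. SAP 7.1 separately reports "those who discontinued treatment early along with the reason for early treatment discontinuation". Protocol 9.3.3 asks for compliance by treatment group but gives no formula.

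**The concern.** The formula is introduced as a restatement of the worded definition, but its numerator is in doses and its daily multiplier is in capsules. Both documents keep the two units apart, so the two sentences cannot both be followed.

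A programmer who applies the formula as written would produce a compliance table in which every participant dosed as scheduled appears in the lowest class. The middle class, where on-schedule participants belong, would be out of reach. Part 1 has safety and tolerability as its primary objective, and a reader interprets those results against how much drug was taken. A table that makes full dosing look like 25% adherence would mislead that reading.

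**Working it through.** **Inputs.** The course is 14 doses, twice daily, over 7 days (SAP 3). One dose is 1,000 mg in 250 mg capsules (Protocol 7.1.1.2). The full course is 14 doses or 56 capsules (Protocol 6.3.2). Let E be Study Drug Exposure in calendar dates (SAP 6). The classes are <80%, 80%-120% and >120% (SAP 7.3).

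**Where the 8 comes from.**
- Doses per day: 14/7 = 2. The multiplier 8 is not reproduced.
- Capsules per day: 1,000/250 = 4 per dose, and 4 × 2 = 8. Over 7 days, 8 × 7 = 56, which matches the stated capsule total exactly.

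**The printed formula, 100 × doses / (8 × E).**

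| Doses taken | E = 7 | E = 8 |
|---|---|---|
| 14 | 14/56 = 25.0% | 14/64 = 21.9% |
| 13 | 13/56 = 23.2% | 13/64 = 20.3% |
| 12 | 12/56 = 21.4% | 12/64 = 18.8% |

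With at most 2 doses per date, doses ≤ 2E, so the score is at most 2E/(8E) = 25.0% for any E. Reaching 80% over 7 dates would take 0.8 × 56 = 44.8 doses, or 6.4 per day. Under the worded definition the complete course is 14/14 = 100%.

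**Matching units.** For a complete course of full doses over 7 dates, doses give 14/(2 × 7) = 100% and capsules give 56/(8 × 7) = 100%. The two versions part when doses are partial. A participant taking 3 of the 4 capsules at all 14 doses scores 14/14 = 100% by doses (each counted as taken) but 42/56 = 75.0% by capsules, which is a different class. Protocol 7.3 has the home diary record the amount taken, so partial doses can be captured.

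**Eight calendar dates.** If the first dose is the second of its date, the course runs 1 + 6 × 2 + 1 = 14 doses over 8 dates. With only the unit corrected, a complete course scores 14/16 = 87.5% (in capsules, 56/64 = 87.5%). Capping the denominator at the planned course, min(14, 2E), gives 14/14 = 100%.

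**Who would change class because of the cap.**
- E ≤ 7: 2E ≤ 14, so the cap has no effect.
- E = 8: the uncapped score is below 80% when doses < 0.8 × 16 = 12.8, and the capped score is at least 80% when doses ≥ 0.8 × 14 = 11.2. Only 12 doses meets both, at 12/16 = 75.0% against 12/14 = 85.7%. The two missed doses must lie inside the span, otherwise it would be shorter than 8 dates.
- E = 9, possible only if missed doses are taken later: 14 doses score 14/18 = 77.8% against 100%, and 13 doses score 13/18 = 72.2% against 13/14 = 92.9%.

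**Early stopping.** Any exposure-based denominator ignores doses omitted after the last dosing date. Six doses over 3 dates score 6/6 = 100%, although 6/14 = 42.9% of the planned course was received.

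**The case against.** The best defence is that this is a wording slip that any competent programmer would see through. Eight is exactly the capsules per day, capsules over 8 × exposure gives 100% for a full 7-date course, and a class of 80%-120% makes sense only if on-schedule dosing scores near 100%. A literal run, with everyone at or below 25%, would be noticed at once. Most of this stands: capsules were probably intended. It does not remove the need to correct the line. Both the worded definition and the formula say doses, and SAP 7.3 reports a dose count in the same table, so following the text puts doses in the numerator. The capsule reading also leaves the 8-date course at 87.5%.

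A second objection is that the size of the discrepancy depends on what the treatment period means. If it means the planned 7-day course, someone who takes 6 doses in 3 days should score 6/14 = 42.9% against the printed 6/24 = 25.0%, which is not a fourfold difference. That is correct. The factor of 4 holds when the treatment period is read as the exposure span. For a complete course over 7 dates it holds on either reading.

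A third is that the cap is a separate matter from the unit error. That is also fair, and it is treated here as secondary.

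A reader might infer more than the documents support:
- *That the error reaches the efficacy or per-protocol analyses.* Protocol 9.2 defines the Per Protocol Set by baseline disease criteria and major deviations, and neither document sets a compliance threshold for any analysis set or test.
- *That without a cap only the 12-dose, 8-date pattern can change class.* That requires no extra or make-up doses. The documents do not establish this; both say that dosing continues until the course is finished.
- *That the dose and capsule formulas are interchangeable.* They agree only if every dose is the full 4 capsules.

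**Conclusion.** The concern holds as an internal contradiction in SAP section 6. As printed, the formula gives 25.0% or 21.9% for a complete course over 7 or 8 dates and cannot exceed 25.0% for anyone at or below 2 doses per date. All such participants would be placed in the <80% class. This rests on reading a dose as the documents define it, 14 per course. The SAP's own schedule is enough to show the conflict; the protocol's capsule counts explain where the 8 came from.

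The consequence is small. This SAP covers the end of Part 1, planned at 60 participants, and only the descriptive compliance percentage and its classes are affected. Dose counts, treatment duration and early discontinuation with reasons are reported separately and remain correct. It is probably a unit slip, but it yields a wrong result when followed as written, so it should be corrected.

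The 8-date point is narrower. After the unit fix a complete course could still score 87.5%, which stays in the 80%-120% class. The documents do not show how many participants, if any, would change class because of it.

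**What to change.** Replace the formula in SAP section 6 with one that uses a single, named unit. Choose one of:

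- 100 × doses taken / (2 × Study Drug Exposure), or
- 100 × capsules taken / (8 × Study Drug Exposure), which also reflects partial doses.

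In the same line, cap the denominator at the planned course, min(14, 2 × Study Drug Exposure) doses or min(56, 8 × Study Drug Exposure) capsules, so that a complete course scores 100% over 7 or 8 dates. The existing classes can stay.

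State the remaining limit: with an exposure-based denominator a participant who stops early can still score 100%. If that could be misread as completion, add doses taken / 14 as the percentage of the planned course received.

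The cost is one line in the SAP. The dose version needs only the dose counts and dates already used. The capsule version needs capsule amounts, so confirm that these are captured for doses given in hospital as well as in the home diary before choosing it. The optional percentage only rescales the dose count that SAP 7.3 already reports.

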- A persistent or significant incapacity or substantial disruption of the ability to conduct normal life functions
- A congenital anomaly/birth defect
- Important medical events that may not result in death, be life-threatening, or require hospitalization may be considered serious when, based upon appropriate medical judgment, they may jeopardize the patient or participant and may require medical or surgical intervention to prevent one of the outcomes listed in this definition. Examples of such medical events include allergic bronchospasm requiring intensive treatment in an emergency room or at home, blood dyscrasias or convulsions that do not result in inpatient hospitalization, or the development of drug dependency or drug abuse.

**Treatment-emergent** – All AEs will be collected from the signing of informed consent until the EOS visit/Day 60. Non-treatment-emergent AEs are defined from the signing of informed consent to randomization. Treatment-emergent AEs (TEAEs) are defined from randomization through Day 28.

Causality or relatedness - A treatment-related AE (TEAE) is defined as any new AE that begins or any preexisting condition that worsens in severity, after informed consent until the EOS visit (i.e., Day 60+2) and is considered by the investigator to be related to ANA001. All AEs and SAEs should have attribution recorded as treatment- or not treatment-related, in the judgment of the site investigator.

- Related: There is a temporal relationship between the study drug and event, and the AE is known to occur with the study drug or there is a reasonable possibility that the study drug caused the AR. Reasonable possibility means that there is evidence to suggest a causal relationship between the study drug and the AE.
- Not related: There is not a reasonable possibility that the administration of the study drug caused the event, there is no temporal relationship between the study drug and event onset, or an alternate etiology has been established.

**Adverse reaction -** An AR is any AE caused by a drug.

**Suspected adverse reaction (SAR)** - An SAR is any AE for which there is a reasonable possibility that the drug caused the AE. For the purposes of the IND safety reporting, "reasonable possibility" means there is evidence to suggest a causal relationship between the drug and the AE. SAR implies a lesser degree of certainty about causality than AR.

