#### 9.3.6.1 Treatment-Emergent Adverse Events

All adverse events reported during the study will be coded using a MedDRA (v21.1) dictionary. Non-treatment-emergent AEs will be captured on the appropriate eCRF and a listing will be generated for the randomized set. Only treatment-emergent AEs (TEAEs) will be summarized in the planned safety analyses. The incidence of treatment-emergent adverse events will be summarized by treatment group and the following:

Preferred term

System organ class and preferred term

System organ class, preferred term and severity

These summaries will be presented for the following subsets:

All adverse events

Serious adverse events

Drug-related adverse events

Adverse events leading to study treatment discontinuation.

For tables reporting adverse events by severity, if a subject has multiple occurrences of an adverse event with the same organ class and preferred term, the most severe event will be presented.

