10.2 Adverse Events Missing Data

Treatment-emergent adverse events (TEAEs) with missing severity will be considered Grade 3 and TEAEs with missing relationship will be counted as drug-related.

In cases where the start date is not complete, the assumption will be made that the adverse event is a treatment-emergent event unless there is evidence to the contrary. The first treatment start date will be used as the AE start date if the start date is missing. Missing adverse event end dates will not be imputed. The adverse event will be assumed to be ongoing if end date is missing.

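### The SAP definition of a TEAE is silent on worsening, so an AE that begins between consent and first dose and increases in grade on drug may be left out of the Part 1 safety tables

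*SAP*

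**What the plan says.** Three rules bear on which AEs count as treatment-emergent.

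- SAP section 6 (Analytic Definitions): "A Treatment-Emergent Adverse Event (TEAE) is any adverse event that occurs on or after first dosing and up through Day 28".
- Protocol 8.1, under its treatment-emergent heading: "Treatment-emergent AEs (TEAEs) are defined from randomization through Day 28". The complementary class is also defined there: "Non-treatment-emergent AEs are defined from the signing of informed consent to randomization".
- Protocol 8.1, under causality, defines a treatment-related AE, again abbreviated TEAE, as "any new AE that begins or any preexisting condition that worsens in severity, after informed consent until the EOS visit" (Day 60+2), if the investigator judges it related to ANA001.

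On reporting, Protocol 9.3.6.1 says "Only treatment-emergent AEs (TEAEs) will be summarized in the planned safety analyses". For the remainder it says "Non-treatment-emergent AEs will be captured on the appropriate eCRF and a listing will be generated for the randomized set". SAP 7.6.1 builds every AE table from TEAEs, including the subsets for drug-related events and for Grade 3 or higher.

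For incomplete dates, SAP 10.2 says "In cases where the start date is not complete, the assumption will be made that the adverse event is a treatment-emergent event", unless evidence points the other way, and adds "The first treatment start date will be used as the AE start date if the start date is missing".

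**The concern.** AEs are collected from consent (Protocol 6.1 and 8.2.1), so the database can hold AEs that began before any study drug was taken. A treatment-emergent definition usually covers two cases: an event that is new after first dose, and an event already present that becomes worse after first dose. The SAP definition states only the first.

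TEAEs are a primary endpoint of Part 1 (Protocol Table 2; SAP 4.2 and 4.3), and the planned size is 30 per arm (Protocol 9.1.1). If on-drug worsening of a pre-dose AE is missed, the Part 1 tables understate toxicity for those participants. Whether it is missed depends on how each site enters a grade increase, which neither document specifies. Two programmers working from the protocol and the SAP could also produce different TEAE counts from the same data.

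**Working it through.** The plan states no figure that depends on this definition, so the check is mainly a comparison of the rules.

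**Step 1. The three rules side by side.**

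| | SAP 6 | Protocol 8.1, treatment-emergent | Protocol 8.1, treatment-related |
|---|---|---|---|
| Window opens | First dose | Randomization | Consent |
| Window closes | Day 28 | Day 28 | Day 60+2 |
| Worsening included | Not stated | Not stated | Yes |
| Relatedness required | No | No | Yes |

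No two columns agree on when the window opens, and only one mentions worsening.

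**Step 2. Onset or any occurrence?** The SAP verb is *occurs*, which alone does not settle the matter. SAP 10.2 points to onset: for incomplete dates it decides TEAE status through the start date, and it replaces a missing start date with the date of first treatment. That default helps only when the date is incomplete; a complete pre-dose start date stays pre-dose. SAP 6 also gives concomitant medication an explicit carry-over clause for drugs begun before first dose and continued, and has no counterpart for AEs.

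**Step 3. Run one event through the rules.** As an illustration, take Grade 1 nausea, not attributed to COVID-19, that starts after consent and before randomization and reaches Grade 3 on Day 3.

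- *Kept as one record with its original start date.* It is not a TEAE under the start-date reading of the SAP, and the protocol's timing rule classes it as non-treatment-emergent. It appears in a listing but not in the TEAE or Grade 3 or higher tables. If the investigator calls the worsening related, it meets the protocol's treatment-related definition, yet it is missing from the SAP drug-related table, which is a subset of TEAEs.
- *Worsening entered as a new record dated Day 3.* It meets the SAP definition and appears in every relevant table.

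The clinical course is the same and the tables differ. SAP 7.6.1 says a continuing AE is counted once per participant, but not whether one continuing from before first dose qualifies when it worsens.

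**Step 4. Onset between randomization and first dose.** Such an event is a TEAE under the protocol's timing rule. Under the start-date reading it is not one in the SAP. It also falls outside the protocol's listing rule, because that rule covers the class ending at randomization.

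**Step 5. How wide is the gap?** Screening begins at consent (Protocol 5.2), and dosing is to start within about 36 hours of screening (Protocol 4.1 and 6.3); screening and Day 1 may fall on the same day. COVID-19-related events are not recorded as AEs unless serious (Protocol 8.1). Laboratory results are summarised separately by highest CTCAE grade (SAP 7.6.2).

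**Step 6. Size per participant.** 1/30 = 0.033, or 3.3 percentage points of a Part 1 arm. This applies in full to a table row only if the participant has no other qualifying event in that row. The documents give neither the frequency of pre-dose AEs nor the frequency with which they worsen, so no total can be calculated.

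**The case against.** The strongest reply is that silence is not a rule of exclusion. A reader might infer that every AE present before dosing that worsens on drug is barred from all TEAE tables. The documents do not support that. The SAP does not say *starts*, its start-date working has to be inferred from the missing-data rule, and a worsening entered as a new post-dose record would be tabulated. This stands, and it is why the point is that such events may be omitted, not that they are.

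A reader might also infer that the gap removes the drug's expected gastrointestinal effects, because nausea, vomiting and diarrhea are also presenting COVID-19 symptoms. That does not follow. Presenting symptoms are collected as medical history (Protocol 6.1), and non-serious COVID-19 events are not AEs. Such a symptom would normally have no pre-dose AE record. If it worsened and was attributed to drug, its first AE record would be post-dose and would count.

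The start of Part 2 does not rest on these tables alone either. The DMC reviews unblinded data, and its emergency-meeting trigger is AEs leading to discontinuation of study drug, with no TEAE restriction (Protocol 4.1, 6.6.2 and 11.1). Reasons for stopping treatment are tabulated separately (SAP 7.1), and AEs starting before randomization are listed. These backstops limit the harm, but they do not make the reported endpoint reproducible.

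Finally, the SAP is written to protocol Version 4.0 and the protocol supplied is Version 5.0. Part of the mismatch could therefore come from the version difference. The SAP's own omission of worsening does not depend on it.

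**Conclusion.** The point holds in a limited form. The SAP definition does not address worsening, its date handling works from onset, and no rule says how a grade increase is recorded. An AE that begins between consent and first dose and worsens on drug may therefore be absent from the TEAE, Grade 3 or higher and drug-related tables, depending on site practice. Separately, Protocol 8.1 uses one label for two incompatible rules, and neither agrees with the SAP.

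The reach is small: mainly AEs arising in a window of about 36 hours that are serious or unrelated to COVID-19, and that are kept under a single record. Each affected participant is 3.3 points of a 30-participant arm. Any overall percentage-point loss would rest on guessed rates, and none is claimed. The conclusion assumes that TEAE status is programmed from the AE start date, as SAP 10.2 indicates. The correction is worth making because it concerns a primary safety endpoint, the definitions contradict each other, and the remedy is cheap.

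**What to change.** - In SAP 6 and Protocol 8.1, define a TEAE as an AE that starts on or after first dose, or that started earlier and increases in CTCAE grade on or after first dose. Keep the existing Day 28 end. Tabulate the event at its highest on-treatment grade.
- Use first dose as the single window start in both documents, and extend the protocol's non-treatment-emergent class to first dose so that its listing leaves no gap.
- State in the protocol and the eCRF instructions that a grade increase after first dose is recorded with its own date.
- Remove the TEAE abbreviation from the treatment-related definition in Protocol 8.1.
- Align the SAP with the current protocol version.

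The cost is a few definition sentences, a small data-entry rule for sites and possibly slightly higher TEAE counts. If data have already been collected, AEs with a pre-dose start date would need a query on later grade changes, made while still blinded. Design, sample size and efficacy analysis are unaffected.
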